3.4.2. Demographics, Baseline, and Medical History

The demographic variables that will be collected include sex, race, ethnicity, height, weight, and date of birth. Age at the time of vaccination (in years) will be derived based on birthday. For example, if the vaccination date is 1 day before the participant's 86th birthday, the participant is 85 years old. The standard unit (cm) for height should be used. All other nonstandard units should be converted to cm, rounded to 2 decimal places. Similarly, the standard unit of weight (kg) should be used. All other nonstandard units should be converted to kg, rounded to 2 decimal places. BMI will be derived as a ratio of body weight in kilograms (kg) to the square of the body height in meters (m) and rounded to 2 decimal places; the unit for BMI is kg/m².

The N-binding antibody test will be performed by the central laboratory on each blood sample to establish prior exposure to SARS-CoV-2 up to each time point.

Medical history of clinical significance will be collected and categorized according to the current version (at the time of reporting) of MedDRA.

3.4.3. E-Diary Completion

An e-diary will be considered transmitted if any data for the local reactions and systemic events are present for any day. If all data are missing for all items (local reactions and systemic events) on the e-diary for all 7 days after vaccination, then the e-diary will be considered not transmitted. An e-diary will be considered transmitted for a given day if any data are present for that day. The following variables will be derived:

- E-diary data transmitted on each day of Day 1 through Day 7.
- E-diary data transmitted on any day of Day 1 through Day 7.

- E-diary data transmitted at both Day 1 and Day 2.
- E-diary data transmitted from Day 1 through Day 3.
- E-diary data transmitted from Day 1 through Day 4.
- E-diary data transmitted from Day 1 through Day 5.
- E-diary data transmitted from Day 1 through Day 6.
- E-diary data transmitted for all 7 days.

3.4.4. Nonstudy Vaccines

Any nonstudy vaccinations received from 28 days prior to study enrollment through the conclusion of study participation will be collected.

Nonstudy vaccinations will be categorized according to the latest version (at the time of reporting) of the WHODD.

3.5. Safety Endpoints

3.5.1. Adverse Events

AEs are classified into 1 of 3 tiers. Different analyses will be performed for different tiers (refer to [Section 6.6.1](#)).

- Tier 1 events: These are prespecified events of clinical importance. As of this SAP amendment, no Tier 1 events have been identified for the combination vaccine. However, Guillain-Barre syndrome (occurring from Day 1 through Day 43 after vaccination), polyneuropathy (occurring from Day 1 through Day 43 after vaccination), and atrial fibrillation (occurring from vaccination through the 1-month follow-up visit) have been identified as Tier 1 events for RSVpreF. The RSV program Tier 1 list of MedDRA PTs is maintained by the Safety Risk Lead in the Custom Adverse Event Term List System (CAETeLiSt) and referenced in the Safety Surveillance Review Plan for the program. The current list of Tier 1 events referenced by this study for RSVpreF should be confirmed to ensure that appropriate Tier 1 events will be used to produce final tables/graphs before conducting an analysis.
- Tier 2 events: Considering this is a Phase 1/2 study with no placebo-controlled groups, no Tier 2 event will be defined.
- Tier 3 events: These are events that are neither Tier 1 nor Tier 2 events.

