8.4.1. Time Period and Frequency for Collecting AE and SAE Information

The time period for actively eliciting and collecting AEs and SAEs (“active collection period”) for each participant begins from the time the participant provides informed consent, which is obtained before the participant’s participation in the study (ie, before undergoing any study-related procedure and/or receiving study intervention), through and including Visit A102 (1-month follow-up visit), per the SoA in the substudy appendix.

Record any AEs that occur within the 48 hours after the blood draw.

SAEs will be collected from the time the participant provides informed consent through and including Visit A103 (6-month follow-up visit), per the SoA in the substudy appendix.

Follow-up by the investigator continues throughout the active collection period and until the AE or SAE or its sequelae resolve or stabilize at a level acceptable to the investigator.

When a clinically important AE remains ongoing at the end of the active collection period, follow-up by the investigator continues until the AE or SAE or its sequelae resolve or stabilize at a level acceptable to the investigator and Pfizer concurs with that assessment.

For participants who are screen failures, the active collection period ends when screen failure status is determined.

If the participant withdraws from the study and also withdraws consent for the collection of future information, the active collection period ends when consent is withdrawn.

If a participant permanently discontinues or temporarily discontinues study because of an AE or SAE, the AE or SAE must be recorded on the CRF and the SAE reported using the Vaccine SAE Reporting Form.

Investigators are not obligated to actively seek information on AEs or SAEs after the participant has concluded study participation. However, if the investigator learns of any SAE, including a death, at any time after a participant has completed the study, and they consider the event to be reasonably related to the study intervention, the investigator must promptly report the SAE to Pfizer using the Vaccine SAE Reporting Form.

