- The investigator or appropriately qualified designee reviews the reactogenicity e-diary data online following vaccination to evaluate participant compliance and as part of the ongoing safety review. Daily review is optimal during the active diary period.

10.11.10.7.2. Visit A102 – 1-Month Follow-Up Visit (After Vaccination) – 28 to 35 Days After Visit A101

- Record AEs as described in [Section 8.4](#).
- Record nonstudy vaccinations as described in [Section 10.11.8.7](#).
- Record prohibited medication use as described in [Section 10.11.8.7.1](#).
- Verify understanding of and compliance with protocol requirements for contraception as described in [Section 5.3.1](#).
- Collect a blood sample of approximately 50 mL for immunogenicity testing.
- Review the participant's reactogenicity e-diary data. Collect stop dates of any reactogenicity e-diary events ongoing on the last day that the reactogenicity e-diary was completed and record stop dates in the CRF if required.
- If not already completed, collect the participant's e-diary or assist the participant with removing the study application from their own personal device.
 - Ensure all e-diary data have been transferred prior to e-diary deactivation or removal of the app.
- Record any AEs that occur within the 48 hours after the blood draw as described in [Section 8.4.1](#).

10.11.10.7.3. Visit A103 – 6-Month Telephone Contact – 175 to 189 Days After Visit A101

- Contact the participant by telephone.
- Record SAEs as described in [Section 8.4](#).
- Record nonstudy vaccinations as described in [Section 10.11.8.7](#).
- Record prohibited medication use as described in [Section 10.11.8.7.1](#).

- Complete the source documents.
- The investigator or an authorized designee completes the CRFs.

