6.6. Safety Summaries and Analyses

6.6.1. Adverse Events

For all of the AEs categorized in [Section 3.1.2.3](#), each individual AE will be categorized by MedDRA and descriptively summarized by vaccine group.

AEs are classified into 1 of 3 tiers ([Section 3.5.1](#)). For Tier 1 events, 2-sided 95% CIs for the difference between the comparator group and reference group in the percentage of participants reporting the events, based on the Miettinen and Nurminen³ method, will be provided. In addition, the asymptotic p-values will also be presented for the difference between groups in the percentage of participants reporting the events, based on the same test statistic and under the assumption that the test statistic is asymptotically normally distributed. AE displays will be sorted in descending order of point estimates of risk difference within the SOC. The analysis on Tier 1 events is planned for comparing Groups 4, 6, and 7 pooled (RSVpreF coadministered or administered alone) and Groups 1, 2, 4, 6, and 7 pooled (RSVpreF combination or coadministered or administered alone), to Groups 3 and 5 pooled (Bivalent BNT162b2 or QIV administered alone, reference group).

It should be recognized that most studies are not designed to reliably demonstrate a causal relationship between the use of a pharmaceutical product and an AE or a group of AEs. Except for select events in unique situations, studies do not employ formal adjudication procedures for the purpose of event classification. As such, safety analysis is generally considered an exploratory analysis and its purpose is to generate hypotheses for further investigation. The 3-tier approach facilitates this exploratory analysis.

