7. INTERIM ANALYSES

7.1. Introduction

7.1.1. Analysis Timing

No formal interim analysis will be conducted for this study phase.

The primary analysis will be performed on safety and immunogenicity data through 1-month postvaccination visit (ie, Visit A102); all type I error will be spent at this analysis. Once this analysis has been completed, study participants and the study team may be unblinded to study intervention allocation. The 6-month safety data will be summarized when they become available.

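### The Tier 1 window for Guillain-Barré syndrome and polyneuropathy runs to Day 43, but nonserious events are actively collected only to Visit A102 (about Day 29 to 38)

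*SAP*

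**What the plan says.** SAP 3.5.1 names three Tier 1 events for RSVpreF and gives each a time window:

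- "Guillain-Barre syndrome (occurring from Day 1 through Day 43 after vaccination"
- "polyneuropathy (occurring from Day 1 through Day 43 after vaccination"
- "atrial fibrillation (occurring from vaccination through the 1-month follow-up visit"

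SAP 6.6.1 compares these events between pooled groups: "For Tier 1 events, 2-sided 95% CIs for the difference between the comparator group and reference group", with asymptotic p-values. The AE analyses use the safety population, which SAP 4 defines as everyone who received study intervention, whatever the length of follow-up.

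Protocol 8.4.1 sets the collection periods. Active collection of adverse events runs "through and including Visit A102 (1-month follow-up visit), per the SoA in the substudy appendix". For serious events it is longer: "SAEs will be collected from the time the participant provides informed consent through and including Visit A103 (6-month follow-up visit". The procedure list for the 6-month call (Protocol 10.11.10.7.3) says "Record SAEs as described in" Section 8.4 and does not mention nonserious events. Protocol 8.4.1 and 10.11.10.7.2 also ask for adverse events in the 48 hours after the blood draw.

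On timing, SAP 7.1.1 states: "The primary analysis will be performed on safety and immunogenicity data through 1-month postvaccination visit (ie, Visit A102". SAP 6.1.4.1 adds the final database release as a second analysis point for AEs and SAEs. SAP 6.6.1 does not say at which of the two the Tier 1 table is produced.

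**The concern.** A percentage labelled Day 1 to Day 43 implies that everyone in the denominator was observed for the event over those 43 days. Here the row would be a mixture: all events up to a participant-specific A102 date, then only serious ones. Atrial fibrillation, defined in the same SAP sentence, has a window that ends where adverse event collection ends, so the mismatch is confined to the two neurological events.

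At stake is how the table is read. Tier 1 is the only between-group safety comparison for which the SAP specifies p-values, and the SAP version history says these events were added at the regulator's request. A reader who takes the label at face value would credit the trial with more observation than it planned.

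**Working it through.** The documents state no coverage or power figure for Tier 1, so there is none to reproduce. The check is day arithmetic.

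**Inputs**

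- Tier 1 window: Day 1 to Day 43, so 43 study days (SAP 3.5.1).
- Visit A102: 28 to 35 days after A101, with Day 1 as the day of vaccination (Protocol 10.11.3).
- Possible extension: 48 hours, or 2 days, after the A102 blood draw (Protocol 8.4.1 and 10.11.10.7.2).

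**Formula.** Last observed study day L = days after vaccination + 1 (+ 2 if the 48-hour instruction covers all adverse events). Unobserved share = (43 − L) / 43.

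| A102, days after vaccination | 48-hour extension | L | Days not covered | Share of 43 |
|---|---|---|---|---|
| 28 | no | 29 | 14 | 32.6% |
| 35 | no | 36 | 7 | 16.3% |
| 28 | yes | 31 | 12 | 27.9% |
| 35 | yes | 38 | 5 | 11.6% |

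Over both readings, 5 to 14 days (12% to 33%) are not covered. No on-schedule visit reaches Day 43.

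**Off-schedule visits.** For the immunogenicity analysis SAP 4 accepts blood drawn 27 to 42 days after vaccination. A draw at 42 days is study Day 43 and leaves no gap; one at 27 days is Day 28 and leaves 15 of 43 days (34.9%), before any 48-hour extension.

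**From days to events.** Only nonserious events with onset in the gap are exposed. If onset is uniform over the window (assumption) and a proportion p of cases is nonserious (not given in the documents), the share of all window events outside active collection is p × (5/43 to 14/43):

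- p = 1: 12% to 33%
- p = 0.5: 6% to 16%
- p = 0.25: 3% to 8%

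**Expected counts.** Protocol 2.3.1 reports one Guillain-Barré and one Miller Fisher case in Study C3671013, which Protocol 2.2.3.2 says enrolled over 37,000 participants randomized 1:1. If both cases were RSVpreF recipients (assumption; about 18,500 people), the rate is 2 / 18,500. In the 5 × 150 = 750 planned participants in the groups receiving RSVpreF, that gives 750 × 2 / 18,500 = 0.08 expected cases. Even if every case were nonserious, the share falling in the largest gap would be 0.08 × 14/43 = 0.03. The documents give no rate for polyneuropathy.

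**The case against.** The strongest reply is that the protocol does not clearly shut off late nonserious cases. The schedule of activities (Protocol 10.11.3) ticks collection of AEs and SAEs, as appropriate, at A103. Protocol 8.4.8 lists Guillain-Barré syndrome and acute polyneuropathy as events of special interest without a time limit, and SAP 3.1.2.3 derives such events over the whole substudy. Participants are also told to contact the site about medically attended events, with no end date. So a reader might infer that these cases have no route into the data at all, and that goes too far: late collection is ambiguous rather than absent. But none of this sets up active collection. Protocol 8.4.8 routes events of special interest through the periods of 8.4.1, the A103 procedure lists serious events only, and the SAP's own list of events of special interest omits both conditions.

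Second, the affected set is narrow. Serious cases are collected to 6 months, the SAE definition (Protocol 10.3.2) covers hospitalization, significant disability and important medical events, and the sponsor can reclassify a nonserious event as serious (Protocol 8.4.1.2). This stands, and it is why nonserious polyneuropathy is the main exposure. A reader might also infer from SAP 7.1.1 that the safety analysis stops at A102 for good; SAP 6.1.4.1 and the planned 6-month summary contradict that.

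Third, SAP 6.6.1 describes safety analysis as generally exploratory, no success criterion uses Tier 1, and the collection schedule is identical in all groups. This also stands. The inference that the comparison is biased between groups is not supported, and neither is a claim that the table cannot be compared with other Day 43 figures, since the documents do not show how such figures were collected.

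**Conclusion.** The stated window and the collection period do not agree and should be reconciled. For an on-schedule A102, about 5 to 14 of 43 days (12% to 33%) are not actively observed for nonserious Guillain-Barré syndrome or polyneuropathy, in practice chiefly the latter. This rests on the scheduled visit window and on reading Protocol 8.4.1 and the A103 procedure as governing what is collected at 6 months; an off-schedule visit can widen or close the gap for an individual. The percentage is a share of days. It becomes a share of nonserious events only under uniform onset, and a share of all events only with an assumed nonserious fraction.

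The consequence is under-ascertainment and a mislabelled window in an exploratory comparison. Serious cases enter at the final database release. The expectation of few events is supported by the documents' figures for Guillain-Barré syndrome; for polyneuropathy it is a judgement. Severity is minor.

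**What to change.** Reconcile SAP 3.5.1 with Protocol 8.4.1 in one of two ways.

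1. **Match the window to collection.** Report all Tier 1 Guillain-Barré and polyneuropathy events from vaccination through A102, as already done for atrial fibrillation, and add a separate Day 1-43 row limited to SAEs, produced at the final database release. The second row keeps the serious cases after A102 that a plain truncation would drop. Cost: SAP wording, one extra table row and a shorter stated window for the all-events row.
2. **Match collection to the window.** Keep Day 43 and add one question to the A103 call that records any Guillain-Barré syndrome or polyneuropathy with onset through Day 43, regardless of seriousness. Cost: a line in the protocol's A103 procedure and call script, and some recall error at 6 months. Protocol 10.11.8.2.1 allows participants to be unblinded between A102 and A103, so some answers may be given with knowledge of the vaccine received; the report should say so.

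Under either option, SAP 6.6.1 should state which data release supplies the Tier 1 table. A footnote alone would disclose the mixture but would not separate the all-events count from the serious-only count.

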3.5.2. Vital Sign Data

The temperature collected before the vaccination will only be used to assess any potential protocol deviation for vaccination temporary delay. Similarly, pulse rate and seated blood pressure are collected to ensure that participants meet eligibility for vaccination. Therefore, these will not be included as a baseline variable.

3.5.3. Myocarditis or Pericarditis

Any study participant who reports acute chest pain, shortness of breath, palpitations, or any other symptom(s) that might be indicative of myocarditis or pericarditis within 28 days after vaccination must be specifically evaluated. ECG and measurement of troponin will be performed locally for further evaluation. These events will also be entered as AEs, which will link with signs and symptoms of potential cardiac disease by AE ID in the CRF. AE PTs will be used to determine if these cases are AESIs or not.

The following variables will be derived for these assessments and the derivation will be based on AE PTs:

Cases	Derivation
Cases reported as myocarditis or pericarditis (AESIs)	AE PT included in “autoimmune myocarditis,” “autoimmune pericarditis,” “carditis,” “chronic myocarditis,” “eosinophilic myocarditis,” “giant cell myocarditis,” “hypersensitivity myocarditis,” “immune-mediated myocarditis,” “immune-mediated pericarditis,” “myocarditis,” “myopericarditis,” “pericarditis,” “pericarditis adhesive,” “pericarditis constrictive,” or “pleuropericarditis” with symptom onset within 28 days after vaccination.
Cardiac illness visits only (potential myocarditis/pericarditis only)	AE PT not above, but with a nonmissing signs and symptoms page with symptom onset within 28 days after vaccination.

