8.4.8. Adverse Events of Special Interest

The following events are considered AESIs:

- Confirmed diagnosis of influenza.
- Confirmed diagnosis of RSV infection.
- Confirmed diagnosis of myocarditis or pericarditis occurring within 4 weeks after vaccination. See [Section 10.11.10.7.5](#).
- Confirmed COVID-19 diagnosis (clinical signs/symptoms per the CDC⁶² and positive SARS-CoV-2 NAAT or rapid antigen test result).
- Diagnosis of Guillain-Barré syndrome.
- Diagnosis of acute polyneuropathy without an underlying etiology.
- Diagnosis of atrial fibrillation.
- Preterm delivery (delivery at <37 0/7 weeks' gestation).
- Diagnosis of a hypertensive disorder of pregnancy.
- Details of the AESIs listed above are further defined in the investigator site file.

AESIs are examined as part of routine safety data review procedures throughout the clinical trial and as part of signal detection processes. Should an aggregate analysis indicate that these prespecified events occur more frequently than expected, eg, based on epidemiological data, literature, or other data, then this will be submitted and reported in accordance with Pfizer's safety reporting requirements. Aggregate analyses of safety data will be performed on a regular basis per internal SOPs.

All AESIs must be reported as an AE or SAE following the procedures described in [Sections 8.4.1](#) through [8.4.3](#). An AESI is to be recorded as an AE or SAE on the CRF. In addition, an AESI that is also an SAE must be reported using the Vaccine SAE Reporting Form.

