10.11.10.5. Stopping Rules

The following stopping rules are in place for Substudy A participants, based on review of AEs, ECG, and laboratory data, and apply to study vaccination (Day 1) through Day 28. These data will be monitored on an ongoing basis by the investigator (or medically qualified designee) and sponsor in order to promptly identify and flag any event that potentially contributes to a stopping rule. In the event that sponsor personnel confirm that a stopping rule is met, the following actions will commence:

- The IRC will review all appropriate data.
 - The stopping rule will PAUSE randomization and any further study intervention administration.

- For all participants already vaccinated, all other routine study conduct activities, including ongoing data entry, reporting of AEs, participant e-diary completion, blood sample collection, and participant follow-up, will continue during the pause.

A stopping rule is met if any of the following criteria occur within 28 days after study intervention administration.

Stopping Rule Criteria:

If any participant vaccinated with the combined RSVpreF and bivalent BNT162b2 (original/Omi BA.4/BA.5) vaccine [RSVpreF+BNT162b2] develops:

1. A new ECG abnormality that a cardiologist judges consistent with probable or possible myocarditis or pericarditis, including:
 - Sustained atrial or ventricular arrhythmias
 - Second-degree Mobitz Type II or worse AV block, new bundle branch block
 - Diffuse ST-segment elevation or PR-segment inversion, compatible with pericarditis
2. An abnormal troponin value that is confirmed abnormal on repeat testing, assessed as related to study intervention by the investigator.
3. If ≥ 1 participant vaccinated with any [RSVpreF+BNT162b2] combination develops confirmed myocarditis or pericarditis.
4. If any participant vaccinated with any [RSVpreF+BNT162b2] combination dies.

A charter for the IRC will be prepared and finalized before the first participant provides consent.

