10.11.10.7.5. Additional Procedures for Monitoring of Potential Myocarditis or Pericarditis

Any study participant who reports acute chest pain, shortness of breath, palpitations, or any other symptom(s) that might be indicative of myocarditis or pericarditis within 28 days after study vaccination must be specifically evaluated for possible myocarditis or pericarditis.

In addition to a clinical evaluation, the following should be performed:

- ECG and
- Measurement of the troponin level

If myocarditis or pericarditis is suspected based upon the initial evaluation, the following should also be performed:

- Evaluation by a cardiologist,
- Cardiac echocardiogram and/or
- Cardiac magnetic resonance study

Details of the symptoms reported, and results of the investigations performed, will be recorded in the CRF.

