3.1.2.3. Adverse Events and Serious Adverse Events

Standard algorithms for handling missing AE dates and missing AE severity levels will be applied as described in the Pfizer vaccine data standard rules. Completely missing AE start dates will not be imputed.

The following derivations (yes/no) will be included for each participant:

1. Any AE reported through 1 month after vaccination: If the AE started on the same day of vaccination, and the AE start time is before the vaccination time, then this AE will not be counted. Otherwise, if the AE start time is missing or after the vaccination time, the AE will be included.
2. Any related AE reported through 1 month after vaccination: This is similar to the above except only the related AE is included (excluding the related reactogenicity reported within 7 days after vaccination [[Section 3.1.2](#)]).
3. Any immediate AE (AE start time is within 30 minutes after vaccination) reported after vaccination: Only include AEs that started on the same day of vaccination and with a nonmissing AE start time that is within 30 minutes of vaccination. If the immediate AE is a related reactogenicity event, it would not be included as an immediate AE.
4. Any severe or life-threatening AE reported through 1 month after vaccination.
5. Any AE leading to study withdrawal after vaccination.
6. Any AE leading to death after vaccination.
7. Any SAE reported from vaccination throughout the substudy (including reactogenicity reported in the AE CRF during the e-diary collection period).
8. Any protocol-specified AESI reported from vaccination throughout the substudy. The following are protocol-specified AESIs based on AE PTs:
 - Confirmed diagnosis of influenza.
 - Confirmed diagnosis of RSV infection.
 - Confirmed diagnosis of myocarditis or pericarditis occurring within 4 weeks after vaccination. See PTs provided in [Section 3.5.3](#).
 - Confirmed COVID-19 diagnosis after Visit 1 through the end of the study (clinical signs/symptoms per [CDC¹](#) and positive SARS-CoV-2 NAAT or rapid antigen test result).

Variables 1 through 6 listed above will be derived with 2 approaches: excluding any reactogenicity (but not excluding reactogenicity SAEs) reported in the AE CRF during the e-diary collection period, and with no exclusion at all.

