6.6.2. Myocarditis or Pericarditis

The variable derived in [Section 3.5.3](#) will be summarized with count, percentage, and 95% CI for each vaccine group.

A listing for ECG and measurement of troponin for potential myocarditis/pericarditis evaluation will be provided. Symptoms, ECG, troponin level, cardiac study results, cardiac function evaluation, and final diagnosis results will all be listed for any participants with onset of signs and symptoms within 28 days after vaccination.

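### The cardiac AESI is defined as a confirmed diagnosis, but the SAP builds the tabulated count from reported preferred terms with no confirmation step

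*SAP*

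**What the plan says.** Protocol 8.4.8 lists as an AESI a "Confirmed diagnosis of myocarditis or pericarditis occurring within 4 weeks after vaccination". It does not say what makes a case confirmed, and refers elsewhere: "Details of the AESIs listed above are further defined in the investigator site file". Protocol 10.11.10.7.5 requires an ECG and troponin for any participant with suggestive symptoms within 28 days. It then adds "If myocarditis or pericarditis is suspected based upon the initial evaluation, the following should also be performed", naming a cardiologist's evaluation and an echocardiogram and/or cardiac MR. Symptoms and results go into the CRF.

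SAP 3.1.2.3 repeats the confirmed-diagnosis wording, but introduces its list with "The following are protocol-specified AESIs based on AE PTs" and sends the reader to SAP 3.5.3 for the terms. SAP 3.5.3 states "AE PTs will be used to determine if these cases are AESIs or not", and then "The following variables will be derived for these assessments and the derivation will be based on AE PTs". Its first row, marked as AESIs, takes 15 preferred terms with symptom onset within 28 days. Its second row, for potential cases only, takes any other term where the signs-and-symptoms page has been filled in and onset is within 28 days.

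SAP 6.6.2 gives a count, percentage and 95% CI per vaccine group for these derived variables. Of the work-up it says that "cardiac function evaluation, and final diagnosis results will all be listed", along with symptoms, ECG, troponin and cardiac studies. SAP 2.1 declares no change from the protocol's analysis.

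**The concern.** The same label, AESI, is attached to two different sets of cases. One is defined by a diagnosis that has been confirmed. The other is defined by the dictionary term to which the reported event was coded. The item that separates them, the final diagnosis, is planned for a listing but is not used in the count.

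Myocarditis and pericarditis are named in Protocol 2.3.1 among the key risks of BNT162b2, and cases are described there as very rare. When a group's count is likely to be zero or close to it, a single case decides whether the table shows an event at all. If the table and the listing disagree, the plan does not say which is the protocol-defined AESI count, and that would have to be settled after the data are seen.

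**Working it through.** There is no stated figure to reproduce, because the point turns on how two definitions classify the same case. Take a case with symptom onset within 28 days and cross its coded term with the outcome of the work-up:

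| AE preferred term | Diagnosis confirmed? | AESI under Protocol 8.4.8 | Row under SAP 3.5.3 | Agreement |
|---|---|---|---|---|
| On the list of 15 | Yes | Yes | AESI | Agree |
| On the list of 15 | No | No | AESI | Over-count |
| Not on the list | Yes | Yes | Potential row if the signs-and-symptoms page is filled in, otherwise neither | Under-count |
| Not on the list | No | No | Potential row or neither | Agree |

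The two disagreeing cells follow from the rule as written. The first arises when a suspected case is entered under a listed term and the entry is not revised after the work-up. The second arises when the entry stays at a symptom term, or is coded to a related term outside the closed list. The errors run in opposite directions, so they can also cancel in the total while the wrong cases are counted.

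There is a smaller difference in timing. The SAP dates the onset of symptoms, while the protocol speaks of the diagnosis occurring within 4 weeks. 4 weeks is 28 days, so the window length matches, but the anchor may not.

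The mismatch is not explained by the SAP having been written against the original protocol, because SAP 3.1.2.3 carries the confirmed wording itself. The SAP is therefore also inconsistent internally.

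For scale, use the SAP's own interval (Clopper-Pearson, SAP 5.2.1), with x cases among n participants:

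- lower limit = Beta quantile(0.025; x, n − x + 1), taken as 0 when x = 0
- upper limit = Beta quantile(0.975; x + 1, n − x); when x = 0 this is 1 − 0.025^(1/n)

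The group size of about 150 comes from Protocol 10.11.11.5. The figure of 300 is Groups 1 and 2 together (2 × 150), the recipients of the combined vaccine. SAP 6.6.2 tabulates each group separately, so the pooled line is for orientation only. The case counts are hypothetical.

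| n | x | Rate | 95% CI |
|---|---|---|---|
| 150 | 0 | 0% | 0 to 2.43% |
| 150 | 1 | 1/150 = 0.67% | 0.02 to 3.66% |
| 150 | 2 | 2/150 = 1.33% | 0.16 to 4.73% |
| 300 | 0 | 0% | 0 to 1.22% |
| 300 | 1 | 1/300 = 0.33% | 0.01 to 1.84% |

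Each misclassified case therefore shifts a group's reported rate by 0.67 percentage points, in either direction.

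**The case against.** The best defence is that the gap is mostly closed upstream. Protocol 10.3.3 asks for the diagnosis rather than the symptoms to be recorded wherever possible. Protocol 8.4.3 requires follow-up until the event resolves, stabilizes or is otherwise explained. SAP 3.5.3 links the AE to the cardiac page by AE ID. A confirmed case left under a symptom term would depart from the recording rule. The SAP row is also openly described as reported cases, and counting reported cases tends to overstate a risk rather than hide it. All of this stands and lowers the likelihood of error. None of it makes confirmation a condition of the count.

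A second defence is that the listing in SAP 6.6.2 exposes any misclassified case. That also stands, provided symptom onset was within 28 days. But a listing does not correct the table.

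A third is that confirmation is not defined in these documents, so replacing one field with another may gain little. This has force. The site-file definition cannot be seen here, and nothing shows which criteria govern the final-diagnosis field. It is a reason to tie the confirmed row to that definition and to keep the reported row beside it.

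A reader might infer that the stopping rules could misfire, since one criterion applies when a recipient of the combined vaccine "develops confirmed myocarditis or pericarditis". The documents do not support that. Under Protocol 10.11.10.5 the criteria are monitored on an ongoing basis by the investigator and sponsor, and sponsor personnel confirm that a rule is met. The SAP derivation plays no part.

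A reader might also want the COVID-19 AESI re-derived from symptoms and a positive test, because SAP 3.1.2.3 treats it in the same way. The Substudy A schedule of activities names COVID-19 diagnosis and test results only under medical history at Visit A101. The documents do not show that the postvaccination test data needed for such a derivation are collected.

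**Conclusion.** The mismatch is real and lies in the text. The AESI is a confirmed diagnosis in Protocol 8.4.8 and SAP 3.1.2.3, while the tabulated AESI row is built from preferred terms in SAP 3.5.3, with no declared deviation. The reported count and interval can be wrong in either direction.

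The consequence is limited to descriptive safety output: the table in SAP 6.6.2 and the AESI summary in SAP 6.1.4.2, which is a supplementary analysis. No hypothesis test and no stopping decision depends on it. The size is 0.67 percentage points per misclassified case in a group of 150. The documents give neither an expected number of cases nor a misclassification rate, so any claim about how many cases will be affected would be an assumption.

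The conclusion rests on the SAP derivation being programmed as written, and on the site-file definition of a confirmed case requiring more than the reported term. If that file equated the two, the inconsistency would be one of wording only.

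**What to change.** In SAP 3.5.3 and 6.6.2, keep the preferred-term row and label it as reported (candidate) cases. Add a confirmed AESI row derived from the final diagnosis that SAP 6.6.2 already plans to list, whatever the preferred term, using the investigator site file's definition. Check the candidate cases blinded to vaccine group before database lock. State whether the 28 days run to symptom onset or to diagnosis. Make SAP 3.1.2.3 refer to the confirmed row, so that the AESI summary and the cardiac table agree.

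For COVID-19, at most label the term-based count as reported. No new derivation is proposed.

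The cost is SAP wording, one additional derivation and a case-level check of the few candidates. A reported case with an incomplete work-up would appear only in the reported row, which is why both rows should be shown.
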